### **Analytic Approach**

**Cessation:** The primary outcome (biochemically confirmed, self-reported point-prevalence abstinence at 52 weeks post-TQD) will be analyzed via two strategies. First, we will conduct factorial design analyses using logistic regression with dummy coding that examines

PROTOCOL  
“Quitting Using Intensive Treatment Study (QUITS)”  
PI: [name] and [name] ; UW-CTRI Grant:

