the main and interactive effects of the two factors. Importantly, main effects obtained with dummy coding in 2-factor designs are directly interpretable even in the presence of a significant interaction as long as the interaction effect is included in the model. Thus, main effects will reflect the effects of V+P vs. V-alone, and the effects of 24- vs. 12-week treatment duration. Interaction effects would reveal whether the magnitude of differences in effects of the levels of V treatment varies in a multiplicative manner depending on duration. While we hypothesize that we will see only main effects in this research, interactions would be interpreted via visual inspection (the highest and lowest scores for the interacting treatment combinations should be readily apparent) and via simple effects tests. Second, we will conduct analyses typical of an RCT, which use logistic regression models with dummy coding to contrast each of the three enhanced varenicline treatments (12-week V+P, 24-week V-only and 24-week V+P) with the standard V-based treatment (12-week V-only). The V-only condition will serve as the reference condition because the intent is to determine if any of the enhanced V-based treatments is superior to that condition. Covariates will include sex, race, treatment site, and level of tobacco dependence (FTND item 1). Results will be reported with and without covariate adjustment and the specific effects of sex and race on each outcome will be explored. The same analytic approach will be used for secondary abstinence analyses (e.g., point-prevalence at 6-months and prolonged abstinence). The intent-to-treat principle with the assumption of missing-smoking will be used for abstinence analyses but will be supplemented with sensitivity analyses and multiple imputation for missing data to support scientific rigor. The latter models will assume that 80% of dropouts return to smoking and that abstinence likelihood is related to baseline smoker covariates. Analyses of secondary abstinence outcomes will support scientific rigor by controlling for experiment-wise error in families of related tests. Milestones analyses will be conducted as in our prior research. For instance, latency between initial abstinence and lapsing, and latency between lapsing and relapse, will be computed with Cox proportional hazards regression/survival models.

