**Statistical Power for Primary Outcome:** Power was determined for effects that we prognosticated based upon prior data. Table 4 depicts predicted 52-week abstinence outcomes. We propose an abstinence rate for 12-week V treatment of 25%. This is comparable to that found in Koegelenberg for 12-week V-only treatment (28.8% at 24 weeks follow-up; abstinence rates tend to fall about 5 percentage points from 24 to 52 weeks post-TQD). This abstinence rate is higher than that produced by V-only in our recent clinical trial (19% abstinent at 52 weeks), but somewhat lower than the rates reported in the initial studies on V (52-week rates of about 30%; thus, we set the expected abstinence rate for 12 weeks of V at a mid-point (25%). Table 4 shows that we predict an increase in 52-week abstinence from 12 weeks of V alone (25%) to 34% for 12 weeks of V+P. We believe this increase of 9 percentage points is reasonable and somewhat conservative. It is midway between increases seen by Koegelenberg (15%) and Ramon et al., (5%, in 24-week *continuous* abstinence). Also, a 9 percentage point increase is somewhat less than the boost in abstinence seen with combination NRT vs. NRT monotherapy (36.5% vs. 23.4% at 5+ months as per the PHS Clinical Practice Guideline meta-analyses). In sum, we believe the estimated effect of the P adjuvant at 12-weeks duration seems reasonable and somewhat conservative.

**Table 4.** Predicted Biochemically Confirmed Abstinence Rates at 52-Weeks After the Target Quit Date

	V-only	V+ML	Marginals
12 Weeks of Medication	25.0% (78/312)	34.0% (106/312)	29.5% (184/624)
24 Weeks of Medication	32.0% (100/312)	44.9% (140/312)	38.5% (240/624)
Marginals	28.5% (178/624)	39.4% (246/624)	

Note: Koegelenberg et al., found abstinence rates of 65.1% (with multiple imputation) and 44% (with intent-to-treat) at 6-month follow-up with 12-weeks of V+P treatment. Thus, our predicted rates for V+ML may be conservative. Also, note that the new enrollment goal of 1250 does not divide evenly by 4=312.5, so we rounded down to 312 for the purposes of this chart.

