The predicted data would strongly implicate the additive effects of both 24-week duration and the P adjuvant as being necessary to achieve a marked increase in abstinence over standard V-based therapy. Of course, we might discover instead that a single treatment modification or enhancement confers as much benefit as the combination of the two components (e.g., 24-week V-only produces as much benefit as 24-week V+P). This finding would be welcome to the extent that it means that exceptionally strong results are obtained with the use of only one treatment enhancement, which would save money and perhaps reduce adverse events and burden.

**Statistical Power:** We computed power (via SAS PROC POWER) for the abstinence outcomes in Table 4, assuming  $p < .05$  and two-tailed tests. Power is .88 for the main effect for Duration (n's=625), and .97 for the main effect of Varenicline (V+P vs. V: n's=625). Moreover, power is  $> .99$  for the key hypothesis that the 24-week V+P combination will be superior to 12-weeks of V-only (n's=312). The N used clearly provides some room for error if the predicted outcomes are too sanguine. For instance, we noted above that some data suggest that the increase in abstinence seen with extended medication might be as small as 7%. The proposed N (1250) would permit detection of a 7 point difference with power = .80. Thus, the N proposed would provide good power to detect the proposed effects, and even effects that are modestly weaker, but still of public health significance.

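### The closing claim of good power does not hold for two of the three primary arm contrasts: on Table 4's own rates their power is about .69 and .49, and neither figure is stated

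*Combined protocol and SAP*

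**What the plan says.** Specific Aim 1 looks for the benefit of the patch and of longer treatment in two places: the main effects of the two factors, and direct comparisons of the enhanced conditions with standard 12-week varenicline. Analytic Approach (Cessation) carries this through. The primary outcome, confirmed abstinence at 52 weeks, "will be analyzed via two strategies". The first is a factorial logistic model. The second uses logistic models "to contrast each of the three enhanced varenicline treatments (12-week V+P, 24-week V-only and 24-week V+P) with the standard V-based treatment", which is 12-week varenicline alone.

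Table 4 predicts abstinence of 25.0% for 12-week V-only, 34.0% for 12-week V+P, 32.0% for 24-week V-only and 44.9% for 24-week V+P. (The column is headed V+ML; the surrounding text treats it as V+P.) Each arm has 312 participants.

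The Statistical Power paragraph begins: "We computed power (via SAS PROC POWER) for the abstinence outcomes in Table 4". It assumes the .05 level and "two-tailed tests". It gives:

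- .88 for the Duration main effect and .97 for the Adjuvant main effect, each with 625 per level;
- above .99 "for the key hypothesis that the 24-week V+P combination will be superior to 12-weeks of V-only", with 312 per arm;
- .80 for a 7-point difference, citing the whole-trial N of 1250.

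It ends: "Thus, the N proposed would provide good power to detect the proposed effects, and even effects that are modestly weaker". No power is given for 12-week V+P or 24-week V-only against the standard arm.

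**The concern.** The closing sentence speaks of the proposed effects without limit, and Table 4 proposes three arm-versus-standard differences: 19.9, 9 and 7 points. Only the first has a power figure. The other two are less than half that size and use the same 312 per arm, so they cannot share its power.

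The 7-point statement adds to the problem. The 24-week V-only contrast is itself a 7-point effect (32% v 25%), and a reader could apply the .80 to it. That figure needs about twice as many participants per group as the contrast has.

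At stake is the reading of a null result. If both single enhancements work exactly as predicted, there is still a substantial chance that one or both arm contrasts miss significance. A plan that has declared good power for the proposed effects invites the inference that such an enhancement does not work.

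**Working it through.** **Inputs.** Two-sided alpha .05 (Statistical Power). Cell rates .25, .34, .32, .449 and 312 per arm (Table 4). The note to Table 4 explains that 1250/4 = 312.5, "so we rounded down to 312 for the purposes of this chart". Margins are .295 v .385 for Duration and .285 v .394 for Adjuvant, with 625 per level. No allowance for dropout is needed, because missing is counted as smoking and every randomised participant stays in the denominator.

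**Formula.** Two-sample test of proportions with pooled null variance. With d = p2 − p1 and m = (p1 + p2)/2:

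power = Φ{ [d − 1.96·√(2m(1−m)/n)] / √([p1(1−p1) + p2(1−p2)]/n) }

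**The plan's own arm figure first.** 25% v 44.9%, n = 312: m = .3495, null SE = .0382, alternative SE = .0373. (.199 − .0748)/.0373 = 3.33, so power = .9996. The stated value, above .99, reproduces.

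**The two contrasts with no stated power.**

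- 12-week V+P, 25% v 34%, n = 312: m = .295, null SE = .0365, alternative SE = .0363. (.09 − .0716)/.0363 = 0.51, so power = .694.
- 24-week V-only, 25% v 32%, n = 312: m = .285, null SE = .0361, alternative SE = .0360. (.07 − .0708)/.0360 = −0.02, so power = .491.

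Other standard methods give nearly the same answers:

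| Method | 34% v 25% | 32% v 25% |
|---|---|---|
| Pooled normal | .694 | .491 |
| Wald test on log odds ratio | .691 | .489 |
| Arcsine | .695 | .492 |
| Continuity-corrected | .662 | .455 |
| Simulation (400,000 trials) | .695 | .491 |

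Even a one-sided test, contrary to the plan, would give only .795 and .615.

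**Detectable difference.** Solving the formula for power .80 at n = 312 from a base of 25% gives about 10.3 points, against predicted single effects of 9 and 7. Conversely, 80% power for those effects would need 402 and 652 per arm.

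**Joint behaviour.** Simulating the four arms at Table 4's rates with the shared reference arm: all three contrasts are significant in about 41% of trials. In about 23% only the combination contrast is significant.

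**The 7-point statement.** At 625 per level, power is .783 from a 25% base and .750 from Table 4's 12-week margin of 29.5%. The first is within 2 points of the stated .80, so the statement fits a main effect. The 7-point arm contrast at 312 per arm has .491.

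**Main effects, for comparison.** At 625 per level the formula gives .920 for Duration (stated .88) and .983 for Adjuvant (stated .97). The stated values are somewhat lower than these. Either way, the averaged main effects are well powered on Table 4's rates.

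**The case against.** Several points can fairly be made for the plan.

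- **The closing sentence can be read narrowly.** It ends a paragraph that has just powered three effects (Duration, Adjuvant, combination v standard), and the remark about weaker effects follows directly on the 7-point example. On that reading it claims nothing about the other two contrasts. This is possible, but the text does not say so. Table 4 and its commentary propose the 9-point effect explicitly, and Specific Aim 1 and Analytic Approach give all three contrasts primary standing.
- **The factorial analysis comes first and one contrast is named the key hypothesis.** This stands. A reader might infer that power is given for nothing but the easiest comparison. That would be wrong: both main effects and a 7-point difference are covered. The gap lies among the three arm contrasts.
- **Misreading the trial as showing that only the combination works.** A reader might infer that this is the likely result of low power. The documents do not support going that far, because both analyses are prespecified and would be seen together. In simulated trials where only the combination contrast is significant, both averaged main effects are significant in about 87% and neither in about 0.4%. The misreading is a risk if the arm contrasts are read alone.
- **Multiplicity.** A Bonferroni correction over three contrasts would lower the two figures to .53 and .32. The plan states no such adjustment for the primary contrasts; its experiment-wise control is for secondary abstinence outcomes. These figures are therefore hypothetical and form no part of the point.

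The defence from the main effects also has a condition. Analytic Approach specifies dummy coding with the interaction in the model. If that means 0/1 coding, each so-called main-effect coefficient is the simple effect at the reference level of the other factor. With 12-week V-only as reference, those are the same 312-per-arm comparisons with power .69 and .49. The 625 per level quoted in the power section implies averaging, but the coding as described does not secure it.

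**Conclusion.** The point holds. On the plan's own rates, sample size and test level, two of the three primary arm contrasts have power of about .69 and .49, and the plan states neither. The general claim of good power for the proposed effects, and for modestly weaker ones, is not met for those two. It is met for the combination contrast and for main effects averaged over the other factor.

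The figures assume Table 4's predicted rates are true, 312 per arm, unadjusted two-sided .05 tests and no gain from covariates. The finding does not show that the trial is underpowered as a whole, that the stated arm figure is miscalculated, or that the arm contrasts should be dropped. It is an omission together with a summary sentence that is too broad.

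**What to change.** In Statistical Power:

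1. State power for all three arm contrasts at 312 per arm: .69 (12-week V+P), .49 (24-week V-only) and above .99 (24-week V+P).
2. Limit the good-power sentence to the two averaged main effects and the combination contrast.
3. Say that the 7-point figure refers to a main effect with about 625 per level.

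In Analytic Approach (Cessation):

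4. Keep all three contrasts as planned and report each with a 95% confidence interval. State that a non-significant single-enhancement contrast is to be read together with the corresponding main effect and is not evidence that the enhancement fails.
5. Specify that main effects are averaged over the other factor, by effect (−1/+1) coding or equivalent marginal contrasts, and are not the 0/1 coefficients from the interaction model. Without this, item 4 leans on power that the analysis may not deliver.

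The cost is a few sentences and a less favourable stated power. No more participants are needed, and the hierarchy of analyses is unchanged.

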### **Protection of Human Subjects**

#### **Risks to the Participants**

***Human Subjects Involvement and Characteristics:*** Up to 1100 adult smokers will be consented from the community in order to enroll (randomize) at least 1250 participants (up to 1300). Participants must: plan to stay in the area for the next 12 months, ability to read and write in English, smoke  $\geq 10$  cigarettes per day, be  $\geq 18$  years old, desire to quit smoking but not be

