Building on our recent NHLBI-funded publication in *JAMA* that described the modest effectiveness of varenicline pharmacotherapy, the proposed research will use a factorial design to evaluate two different medication use strategies on their ability to markedly enhance varenicline effectiveness in a large cohort of current smokers. Smokers (N=1250) will be randomly assigned to one of two levels for each of two factors: 1) an Adjuvant factor (varenicline + placebo patch versus varenicline + nicotine patch), and 2) a Duration factor (12 versus 24 weeks of active medication). Thus, this factorial design yields a "standard" varenicline treatment (12 weeks of active varenicline and 12 weeks of placebo varenicline + 24 weeks of placebo patch), and 3 *enhanced* treatments: 1) 12 weeks of active varenicline and 12 weeks of placebo varenicline + 24 weeks of active patch, 2) 24-weeks of active varenicline + 24 weeks of placebo patch, and 3) 24 weeks of active varenicline + 24 weeks of active patch. Both treatment modifications, longer duration therapy and use of a nicotine replacement therapy (NRT) adjuvant, have produced some quite promising effects. However, in both cases these modifications have been little researched, their effects are not *consistently* positive, and they have not been implemented in a potentially optimal manner. We will implement each modification in an innovative manner designed to enhance its effectiveness. In addition, all participants will be given counseling that supports adherent medication use and that is readily translatable to healthcare settings. The scientific rigor of this work will be enhanced by the use of placebo medication, a large sample, and a factorial design. The latter will allow us to test both the main and interaction effects of the experimental factors. We will also be able to compare each enhanced treatment with standard 12-week varenicline-only therapy to determine whether any of these medication use strategies significantly enhances treatment effectiveness. Outcomes will include long-term smoking abstinence (52 weeks), cost-effectiveness, adverse events, and withdrawal severity. This design will allow us to evaluate two major pharmacotherapy strategies (an NRT adjuvant, extended duration) that yield four distinct varenicline-based treatments. Specific aims of this research are:

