### **Recruitment & Study Entry**

We will recruit participants via multi-media methods (i.e., TV, radio, newspapers and newsletters and other print media, flyers, referral cards, minority outreach, emails to UW employees, social media such as Facebook, and earned media), which we have previously used very successfully. Within 1 week, respondents will be called, screened, and potentially eligible smokers will be scheduled to attend a group orientation session. At the Orientation session, interested individuals will be introduced to the study, have a chance to ask questions and provide written informed consent. Participants will complete a final inclusion/exclusion assessment and complete the baseline assessments. Randomization to a treatment condition will also occur at the Orientation (see Table 2), with stratification on sex, site, dependence, and race.

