## **Study Design**

All participants (N=1250) will receive at least 12 weeks of V plus counseling that emphasizes adherent medication use. Participants will also be randomized to one level of each of the two factors: 1) an Adjuvant factor: active P vs. placebo P; and 2) a Duration factor: 24 vs. 12 weeks of active medication.

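### The protocol plans to consent at most 1100 smokers in order to randomise at least 1250, so the consent figure cannot be met together with the sample size

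*Combined protocol and SAP*

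**What the plan says.** The conflict is in Protection of Human Subjects. The paragraph headed Human Subjects Involvement and Characteristics opens as follows: "Up to 1100 adult smokers will be consented from the community in order to enroll (randomize) at least 1250 participants (up to 1300".

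Everywhere else the size is 1250:

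- Study Overview: "Smokers (N=1250) will be randomly assigned to one of two levels for each of two factors".
- Study Design: "All participants (N=1250) will receive at least 12 weeks of V plus counseling".
- Table 4 note: "the new enrollment goal of 1250 does not divide evenly by 4=312.5, so we rounded down to 312".
- Statistical Power: "The proposed N (1250) would permit detection of a 7 point difference", with 625 per factor level for both main effects.

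The order of consent, screening and randomisation is described in two ways. Under Recruitment & Study Entry, people at the Orientation session "have a chance to ask questions and provide written informed consent", then have a final eligibility check, and "Randomization to a treatment condition will also occur at the Orientation (see Table 2". Table 2 agrees. Under Adequacy of Protection Against Risks (Recruitment and Informed Consent), remaining exclusions are checked at Orientation, eligible people take the form home, and they sign it at the start of the first treatment visit.

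**The concern.** The sentence sets a maximum on consents and a minimum on randomisations, and the maximum is the smaller number. Nobody should be randomised without consent, so both clauses cannot be met. If the 1100 is followed, the trial stops short of the size on which its power statements rest. If the 1250 is followed, the number consented exceeds the figure in the human-subjects section. A sample-size figure that fails when followed should be corrected, even though the intended target is clear from the rest of the protocol.

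There is also a secondary question. If 1100 survived from a smaller target, other text written for that target may have survived too, and the power paragraph is the obvious place to look.

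**Working it through.** **1. The counts.** Inputs: 1100 consented, 1250 minimum and 1300 maximum randomised, all from the one sentence.

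- Shortfall against the minimum: 1250 − 1100 = 150, and 150/1250 = 12.0%.
- Shortfall against the maximum: 1300 − 1100 = 200, and 200/1300 = 15.4%.
- Yield needed: 1250/1100 = 113.6% of those consented, or 1300/1100 = 118.2%. Neither is possible.

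No other consent figure, per-site quota or second recruitment source appears that would close the gap. Four cells of 312 give 1248, which agrees with 1250, so 1100 is the outlier.

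**2. The plan's own power figures.** Inputs: Table 4 margins (Duration 29.5% against 38.5%; Adjuvant 28.5% against 39.4%; 24-week combination 44.9% against 12-week varenicline alone 25.0%), two-sided .05. With n per group, p̄ the mean of p1 and p2, and Φ the standard normal distribution function:

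power = Φ{ [ |p1 − p2|·√n − 1.96·√(2·p̄·(1 − p̄)) ] / √(p1(1 − p1) + p2(1 − p2)) }

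Duration, n = 625: (0.09 × 25 − 1.96 × 0.6699) / 0.6669 = 1.405, so power is .920. The protocol states .88.

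Duration, n = 550 (N = 1100): (0.09 × 23.452 − 1.96 × 0.6699) / 0.6669 = 1.196, so power is .884.

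The same formula gives:

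| Comparison | Stated | N = 1250 | N = 1100 |
|---|---|---|---|
| Duration main effect | .88 | .920 | .884 |
| Adjuvant main effect | .97 | .983 | .969 |
| 24-week combination vs 12-week varenicline alone | > .99 | > .999 | .999 |
| 7 points from 29.5% | .80 | .750 | .695 |
| 7 points from 25% | .80 | .783 | .730 |

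Other two-sided forms of the test (unpooled, continuity-corrected, likelihood-ratio) put Duration power at 625 per level between .911 and .921, so the choice of test does not recover .88.

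**3. What this suggests about the 1100.** The stated .88 and .97 both round from the N = 1100 column; at N = 1250 the first does not reproduce. The Table 4 note describes 1250 as new. Both facts point to a target that was raised without updating every number. The evidence is not conclusive. Other N close to 1100 would fit about as well, and the stated .80 for 7 points fits N = 1250 from a 25% base (.783) better than it fits N = 1100.

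**4. The ceiling needed.** Consents = 1300 / (1 − loss between consent and randomisation). The documents give no loss, so the range is an assumption:

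| Assumed loss | Consents for 1300 randomised |
|---|---|
| 0% | 1300 |
| 5% | 1369 (about 1370) |
| 10% | 1445 |
| 15% | 1530 |

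The consent sequence decides where in this range the trial sits. If the final eligibility check follows consent, some loss is possible. If only people already found eligible receive the form, loss from screening could be nil.

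**The case against.** The best defence is that no reader would be misled. The 1250 appears in the same sentence as the 1100 and in four other places, so a study team would see a stale number and carry on. The same paragraph also sets a different minimum daily cigarette count from the Inclusion/Exclusion section (10 against 5), which suggests the whole paragraph was not updated. No estimand, analysis or randomisation rule uses the 1100. This largely stands: the error is in the text and the intended target is not in doubt. It does not make the sentence workable.

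Four stronger readings are tempting and are not supported.

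- *Power collapses.* A reader might infer this from a 12% shortfall. At exactly 1100 randomised, both main effects and the key contrast still reach their stated power (.884, .969, .999). The 7-point claim does lose ground, but from the 29.5% margin it already misses .80 at N = 1250, which is a separate matter.
- *Sites work to 1100, and exceeding it is a protocol deviation.* The figure is study-wide, no section calls it an operating limit, and the same sentence authorises 1250 to 1300 randomised. The limit approved by the review board is not in the documents.
- *Some consented people are bound to be lost before randomisation.* One of the two accounts of study entry gives the form only to people already found eligible, so zero loss from screening belongs in the range.
- *Signing at the first treatment visit explains the figures*, because people randomised at Orientation could then outnumber those who signed. This is a second inconsistency and does not resolve the first: the sentence says people are consented in order to be randomised.

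**Conclusion.** The point holds as an internal contradiction in a sample-size figure. Kept to literally, 1100 consents leave the trial at least 150 (12%) below N = 1250 and 200 (15.4%) below the 1300 maximum. This needs only that everyone randomised has consented; it assumes nothing about loss or power. The consequence is a consent figure that cannot be followed, with little loss against the stated power for the main effects and the key contrast.

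That 1100 came from an earlier target, and that .88 and .97 were computed at that target, is a reasonable inference from the Table 4 note and the recomputation. A reader might take it as established, but the documents do not say so, and the 7-point figure does not fit it.

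**What to change.** - Replace 1100 with a study-wide consent ceiling of at least 1300. Add an allowance for loss between consent and randomisation, state the rate assumed, and give its basis.
- Use the same figure in the application to the review board if that also carries 1100.
- Reconcile the order of consent, screening and randomisation between Recruitment & Study Entry with Table 2 and Recruitment and Informed Consent, since the allowance depends on it.
- Check whether the power figures were computed at N = 1250. If they were not, recompute them, and state the base rate used for the 7-point difference.

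The cost is one corrected number, a wording reconciliation and a rerun of the power calculation. The target of 1250 to 1300 randomised does not change.
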